### 2. Observation Method

Continuous monitoring of vital signs ( $\text{SpO}_2$ , heart rate, blood pressure) during and immediately after intubation.

Post-procedure evaluation of the airway via clinical examination, suctioning

records, and laryngoscopic confirmation when indicated.

Extubation follow-up within 72 hours to identify delayed complications.

Resident self-report questionnaires and supervisor observation to capture psychological or human-factor-related adverse events.

### 3. Recording and Reporting

All adverse events will be recorded in case report forms (CRFs), specifying type, severity, onset time, and outcome.

Serious adverse events (SAEs) will be reported to the institutional ethics committee within 24 hours.

Data will be analyzed to compare incidence rates between the control and PDCA groups.

### 九. Data security monitoring

Clinical research will develop a corresponding data security monitoring plan based on the size of the risk. All adverse events were recorded in detail, properly handled and tracked until they were properly resolved or stable. Serious adverse events and unexpected events were reported to the ethics committee, competent authorities, sponsors and drug supervision and management departments in a timely manner according to the regulations. The main researchers regularly conduct a cumulative review of all adverse events, and if necessary, convene a meeting of researchers to assess the risks and benefits of the study ; research that is greater than the minimum risk will arrange independent data monitors to monitor the research data, and high-risk research will establish an independent data security supervisory committee to monitor the accumulated security data and effectiveness data to make recommendations on whether the research will continue.

### 十. Statistical processing

All statistical analyses were performed using SPSS version 26.0 (IBM Corp., Armonk, NY, USA). Categorical variables, including intubation success rate,

incidence of local airway trauma, extubation failure due to airway injury, and resident satisfaction rate, were expressed as counts and percentages [n (%)], and were compared between groups using the chi-square test ( $\chi^2$  test) or Fisher's exact test, as appropriate. Continuous variables, such as intubation completion time, were tested for normality using the Shapiro–Wilk test. Variables not conforming to a normal distribution were expressed as median (interquartile range) and compared using the Mann–Whitney U test. A two-tailed P value  $< 0.05$  was considered statistically significant.

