## 四、 case selection

### Inclusion Criteria:

- (1) Emergency medicine residents rotating in the emergency department during the study period.
- (2) Residents who are required to perform tracheal intubation as part of clinical training.
- (3) Residents who have completed baseline theoretical and simulation-based airway management training.

① Voluntary participation with written informed consent.

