#### **六. Observation items and detection time points**

##### **1. First-Attempt Success Rate of Tracheal Intubation**

Observation item: Whether residents complete intubation successfully on the first attempt.

Detection time point: Immediately during the procedure, confirmed by chest

rise, end-tidal CO2, auscultation, or chest X-ray.

2. Intubation Completion Time

Observation item: Time required for residents to complete intubation.

Detection time point: Measured in seconds from insertion of the laryngoscope to confirmation of successful tube placement.

3. Incidence of Local Airway Trauma

Observation item: Presence of visible bleeding or mucosal injury during suctioning after intubation.

Detection time point: Within 24 hours post-intubation.

4. Extubation Failure Due to Airway Injury

Observation item: Need for reintubation caused by airway injury (edema, vocal cord paralysis, granulation, or subglottic stenosis).

Detection time point: Within 72 hours post-extubation.

5. Resident Satisfaction With Training

Observation item: Residents' subjective evaluation of the PDCA training program.

Detection time point: At the end of the emergency department rotation, via anonymous questionnaire.

七. standards for efficacy appraisal

1. Primary Efficacy Standard

First-attempt success rate of tracheal intubation is the primary indicator of efficacy.

An intervention is considered effective if the PDCA-trained group demonstrates a statistically significant improvement compared with the control group ( $P < 0.05$ ).

2. Secondary Efficacy Standards

Intubation completion time: A reduction in median time compared with controls indicates improved procedural efficiency.

Incidence of airway trauma and extubation failure: Lower rates suggest enhanced safety and procedural proficiency, even if not statistically significant.

Resident satisfaction score: Higher satisfaction rates reflect better training experience and improved confidence.

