### 3. Comprehensive Appraisal

The PDCA training program will be deemed efficacious if it results in significant improvement in the primary outcome and favorable trends across multiple secondary outcomes.

Statistical analyses will use chi-square tests for categorical variables and Mann-Whitney U test for continuous variables, with  $P < 0.05$  considered statistically significant.

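### The efficacy rule rests on an unadjusted chi-square test, but the protocol does not say whether its 100 cases are residents or intubations; if intubations, repeats by one resident are treated as independent

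*Protocol*

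**What the plan says.** **The test.** The abstract's statistical method and section 十 (Statistical processing) give the same rule: categorical outcomes "were compared between groups using the chi-square test" or Fisher's exact test, two-sided at 0.05. Section 七.3 (Comprehensive Appraisal) repeats it: "Statistical analyses will use chi-square tests for categorical variables and Mann-Whitney U test for continuous variables". None of these places includes a term for the resident or a covariate.

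**The decision.** Section 七.1 (Primary Efficacy Standard) names first-attempt success as the primary indicator and states: "An intervention is considered effective if the PDCA-trained group demonstrates a statistically significant improvement compared with the control group", at P < 0.05. The overall appraisal in 七.3 asks for more: "significant improvement in the primary outcome and favorable trends across multiple secondary outcomes".

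**The unit.** The abstract plans 100 cases and does not define a case.
- Pointing to residents: the case-selection section lists people, for example "Emergency medicine residents rotating in the emergency department during the study period", and the design section assigns residents to groups by the period in which they intubated.
- Pointing to procedures: section 六.1 observes "Whether residents complete intubation successfully on the first attempt" at the time of the procedure. Stage 1 (Plan) speaks of instructors assigning cases to residents, where a case is a patient. It also has beginners start on easier patients and move to harder ones.

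**Mixed levels.** Section 十 groups success with "incidence of local airway trauma, extubation failure due to airway injury, and resident satisfaction rate, were expressed as counts and percentages". Success and trauma arise at each procedure. Satisfaction arises once per resident: "At the end of the emergency department rotation, via anonymous questionnaire".

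**The concern.** A chi-square test needs independent outcomes. Intubations by the same resident share that resident's skill, so their outcomes tend to be alike. If several intubations per resident enter the 2×2 table as separate observations, the test overstates the information in the data and rejects a true null hypothesis too often. The declared efficacy rule is read directly from this test, so its real error rate depends on a unit that the protocol leaves open.

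This is more than a detail left for a later analysis plan. The protocol already names the test and ties the verdict to it, so a plan that analysed the primary outcome differently would depart from the protocol's own efficacy standard.

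A secondary point holds whichever unit is meant. The groups are two non-randomised calendar periods, and the only efficacy test compares them crudely. The protocol excludes residents with more than 50 independent intubations, so it regards prior experience as relevant to performance.

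**Working it through.** **Inputs from the protocol:** 100 cases in total; two-sided level 0.05; unadjusted chi-square or Fisher test; two groups defined by calendar period.

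**Assumed inputs, because the protocol gives none:** 50 intubations per period; m = 1, 2, 5 or 10 intubations per resident, equal across residents; intraclass correlation (ICC) 0.05, 0.10 or 0.20; each resident in one period only.

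**Formulas**
- Design effect: DEFF = 1 + (m − 1) × ICC.
- True two-sided error of the nominal 5% test: 2 × [1 − Φ(1.96 / √DEFF)].
- False claim of improvement: half of that (nominal 2.5%).

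**Starting point: the declared level.** With m = 1, DEFF = 1 and the error is 5.0% two-sided, 2.5% for improvement. One outcome per resident, each in one period only, reproduces the plan's own level.

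**Several intubations per resident**

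| m | ICC | DEFF | Two-sided error | False improvement |
|---|---|---|---|---|
| 2 | 0.05 | 1.05 | 5.6% | 2.8% |
| 2 | 0.10 | 1.10 | 6.2% | 3.1% |
| 2 | 0.20 | 1.20 | 7.4% | 3.7% |
| 5 | 0.05 | 1.20 | 7.4% | 3.7% |
| 5 | 0.10 | 1.40 | 9.8% | 4.9% |
| 5 | 0.20 | 1.80 | 14.4% | 7.2% |
| 10 | 0.05 | 1.45 | 10.4% | 5.2% |
| 10 | 0.10 | 1.90 | 15.5% | 7.8% |
| 10 | 0.20 | 2.80 | 24.1% | 12.1% |

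Worked example, m = 5 and ICC 0.10: DEFF = 1 + 4 × 0.10 = 1.40; 1.96 / √1.40 = 1.656; 2 × [1 − Φ(1.656)] = 0.098.

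**Simulation check.** Beta-binomial data were simulated with an assumed success rate of 0.70, 50 per period and 40,000 runs. Two-sided rejection for ICC 0.05/0.10/0.20 was 5.6/6.1/7.1% at m = 2, 7.1/9.7/14.9% at m = 5 and 10.6/15.8/25.1% at m = 10. With independent intubations it was 5.0%.

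**Residents seen in both periods.** Let f be the share of residents in both periods and c the correlation of a resident's effect between periods. Then DEFF = 1 + (m − 1) × ICC − f × c × m × ICC. The reduction depends on c, which the protocol does not give.
- c = 1, f = 0.8, m = 5: DEFF = 1 and the error is 5.0%.
- c = 0.5, f = 0.8, m = 5: DEFF = 1 + 2 × ICC, and the error is 6.2-9.8%.
- c = 0.5, f = 1: the error is 5.9-8.6% at m = 5 and 7.4-14.4% at m = 10.

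Overlap with positive c therefore lowers the inflation, but no share of overlap can be named at which it ends.

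**Interval width.** A confidence interval that respects the clustering is wider by a factor √DEFF: 1.10-1.34 at m = 5 and 1.20-1.67 at m = 10, before any small-sample correction.

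**The case against.** **The text leans towards residents.** Selection, recruitment and group assignment all concern residents. On that reading the test is valid, and what is missing is a sentence on how several attempts become one outcome. Text not available to this review may also bear on the unit. This stands, and it is why the point is conditional. It does not settle the matter: the primary outcome is recorded per procedure, and the graded progression of patients suggests more than one procedure per resident.

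**Stronger readings that a reader might infer, and that the documents do not support:**
- *That 100 can serve every outcome only if each resident performs exactly one intubation.* One index intubation or one summary value per resident would also give 100. The statistics section never says that its outcomes share a denominator.
- *That enough overlap of residents removes the problem or makes the test conservative.* That holds if a resident's effect is perfectly correlated before and after retraining. At a correlation of 0.5, even full overlap leaves inflation at 5 and 10 intubations per resident.
- *That case mix has biased the comparison, and that the primary analysis must adjust for patient difficulty.* Nothing visible shows that assignment of patients differed between periods. Graded assignment is itself described within the PDCA programme, so adjusting for difficulty could remove part of what is being evaluated.

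**One particular model is a matter of preference.** This also stands. The protocol needs an analysis that accounts for resident, and more than one would do.

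**Conclusion.** The point holds in conditional form and should be fixed; confidence is medium. The protocol fixes the test and the verdict but not the unit.

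With one outcome per resident, each in one period only, the level is as declared. If intubations are counted, the two-sided error is 5.6-7.4%, 7.4-14.4% or 10.4-24.1% at 2, 5 or 10 intubations per resident, against a nominal 5%. These figures rest on assumed cluster sizes, an assumed ICC of 0.05-0.20, 50 intubations per period and no resident in both periods. They apply to the primary efficacy standard in 七.1, not to the overall appraisal in 七.3, which also requires favourable secondary trends.

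The crude comparison of two calendar periods is a limitation under either unit. No size or direction of bias is claimed for it.

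**What to change.** **State the unit of the 100 cases.**

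- *If residents:* define the single outcome per resident, for example one pre-specified index intubation, and keep the chi-square test.
- *If intubations:* record a resident identifier common to both periods and make the primary test of first-attempt success account for resident. Either compare resident-level success proportions, or use a cluster-adjusted method with small-sample correction; the choice must allow for residents who appear in both periods. Treat completion time and airway trauma the same way. Keep the crude chi-square as description.

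**Secondary.** Add a supportive analysis adjusted for residents' prior intubation experience, where it was recorded in both periods. Describe the result as an unrandomised before/after comparison, and say that adjustment does not remove a time trend.

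**Cost.** One sentence on the unit, revised analysis wording and, if intubations are counted, a resident identifier. In that case intervals widen by about 10-34% at 5 intubations per resident and 20-67% at 10, before small-sample correction, and resident identity for the control period has to come from existing records.

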## 十一、Ethics in clinical research

Clinical research will follow the World Medical Congress ' Helsinki Declaration ' and other relevant provisions. Before the study began, the clinical study was carried out after the ethics committee approved the test plan. Before each subject is selected for this study, the researcher has the responsibility to fully and comprehensively introduce the purpose, procedure and possible risks of this study to the subjects or their agents, and to sign a written informed consent form. The subjects should be informed that they have the right to withdraw from the study at any time. Informed consent should be retained as a clinical research document for review. The personal privacy and data confidentiality of the subjects will be protected during the study.

## 十二、Research progress

1. Preparation Phase (September 2024)
  - Finalization of study protocol, ethics committee approval, and trial registration.
  - Recruitment of eligible emergency medicine residents.
  - Baseline data collection and pre-intervention training using traditional methods.
2. Implementation Phase (October 2024 to September 2025)

- Full implementation of the PDCA cycle-based training program.
- Residents rotate through didactic sessions, simulation training, and supervised clinical practice.
- Continuous data collection on intubation performance, adverse events, and resident feedback.

### 3. Evaluation Phase (September 2025)

- Completion of data collection for both control and intervention groups.
- Statistical analysis of primary and secondary outcomes.
- Compilation of results for publication and dissemination.

